1.6 Additional Statistical Analyses

1.6.1 Analysis of Baseline Characteristics

The baseline characteristics of the study group will be presented descriptively. The effects of baseline covariates on the co-primary efficacy measures will be analyzed with univariable and multivariable regression models. Baseline covariates to be explored include (but are not limited to) working memory score from the Reading Span Test, age at implantation, duration of hearing loss, degree of contralateral hearing loss, and gender. Quantitative variables such as age will be presented with mean, standard deviation, median, minimum, and maximum.

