1.9 Missing Data

All efforts will be put forth to ensure near complete follow-up, with particular focus on the assessment of the primary outcomes and occurrence of adverse events. A reminder of subject follow-up due dates will be provided to participating centers to facilitate scheduling of the follow-up visits.

Sensitivity analysis will be conducted to address the potential impact of missing endpoint data using a multiple imputation analysis with 10 imputed datasets. A separate imputation model will be performed for each primary outcome variable (CNC score and average SRT). The predictor variables in the model will include, but are not limited to, the three target variables in the primary endpoint analysis (treatment, period, and sequence), and five auxiliary variables to improve the estimation of missing datapoints (Reading Span score, age, duration of hearing loss, pre-operative sentence score, and duration of hearing aid use). The imputed datasets will then be combined for inference using standard methods such as those available in SAS PROC MIANALYZE or other valid statistical software.

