5.0 Investigational Procedures

5.1 Design Overview

This study will implement a within-subject crossover design with 20 subjects. All subjects will receive each of the treatments – the ACE and FAST strategies. In this repeated measures design, half of the subjects, Group 1, will be mapped with FAST first and the other subjects, Group 2, with ACE first, using formalized mapping procedures. Endpoint speech perception testing, additional to standard clinical testing, will be conducted after 3 months of use with the initial strategy. At the 3-month post initial activation (IA) session, each recipient will be programmed with the crossover strategy. The crossover strategy will then be assessed after 3 months of take-home use at 6 months post IA (refer to Table 1). As indicated in Table 1, fine-tuning of the cochlear implant stimulation levels (i.e. MAP) will occur at 1 week and 1 month after receiving each strategy. Standard clinical testing will also occur at 3 months and 6 months post activation.

The order in which the subjects are programmed with the ACE and FAST strategies will be counterbalanced according to group; Group 1 will start with FAST and Group 2 with ACE. Subjects will be randomly assigned to either Group 1 or 2. Standardized programming procedures will be used to program the FAST and ACE strategies. Subjects will be blinded as to the identity of the strategies.

The study design strikes a balance between providing a reasonable amount of take-home experience with each of the strategies and obtaining outcome comparison data for the strategies within the required timeframe. It is acknowledged that maturational effects are not eliminated with crossover to the alternative strategy at 3 months post IA. The exclusion criteria for enrollment will provide control over some of these variables. To further address maturational effects, subjects' scores from the Reading Span Test (a cognitive test of working

CONFIDENTIAL

memory) will be included as a statistical covariate to understand differences in adaptation that might be associated with working memory.

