5.3 Preoperative Procedures

5.3.1 Visit 1

Visit 1 will take place at the Clinical Sites. A candidacy evaluation will be conducted to determine the subject's eligibility to enroll in the study. The candidacy evaluation will include a hearing history, air conduction and bone conduction audiogram, a CNC word test, and an AzBio sentence test.

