5.5 Postoperative Procedures

5.5.1 Visit 2

Visit 2 will be conducted at the Clinical Sites. Procedures will include initial activation and mapping of the first strategy (Group 1 will receive FAST, and Group 2 will receive ACE). Subjects will be oriented to use of the CP810 processor.

5.5.2 Visit 3

Visit 3 will be conducted at the Clinical Sites. Procedures will include fine-tuning of the initial strategy.

5.5.3 Visit 4

Visit 4 will be conducted at the Clinical Sites. The first battery life questionnaire will be handed out to the subject, and instructions for completing and returning

CONFIDENTIAL

the questionnaire will be provided. Mapping will be conducted for fine-tuning of the initial strategy.

5.5.4 Visit 5

Visit 5 will include endpoint speech perception tests, the Reading Span Test, clinical audiological testing, and programming of the crossover strategy. Depending on the Clinical Site, endpoint speech testing (CNC words and BKB sentences) and the Reading Span Test will be conducted either at the Clinical Site or at the Denver Research & Technology Labs (Cochlear Americas). All programming will be conducted at the Clinical Sites. Since endpoint speech testing will be administered by a clinician blinded to the current treatment, endpoint speech testing and programming will be performed by different clinicians. The crossover strategy will be programmed (Group 1 will receive ACE, and Group 2 will receive FAST), and the acute sound quality ratings will be conducted.

5.5.5 Visit 6

Visit 6 will be conducted at the Clinical Sites. Procedures will include fine-tuning of the crossover strategy.

5.5.6 Visit 7

Visit 7 will be conducted at the Clinical Sites. The SSQ12-C will be completed, and the second battery life questionnaire will be handed out to the subject. Mapping will be conducted for fine-tuning of the crossover strategy.

5.5.7 Visit 8

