Visit 8 will include endpoint speech perception tests, clinical audiological testing, final programming, and fitting with the patient's personal sound processor. Depending on the Clinical Site, endpoint speech testing will be conducted either at the Clinical Site or at the Denver Research & Technology Labs (Cochlear Americas). All programming will be conducted at the Clinical Sites. Since endpoint speech testing will be administered by a clinician blinded to the current treatment, endpoint speech testing and programming will be performed by different clinicians. The subject will be fitted with his or her personal sound processor and the ACE strategy (both groups). Counseling on use of the personal sound processor will be provided.

CONFIDENTIAL

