5.6 Summary of Data Collection Visits

Testing at Clinical Sites								
	Visit 1	Visit 2	Visit 3	Visit 4	Visit 5	Visit 6	Visit 7	Visit 8
Test	Candidacy	Initial Activation (IA)	1 week (post IA)	1M (post IA)	3M (post IA)	3M plus 1 week (post IA)	4M (post IA)	6M (post IA)
Strategy Programming		Program initial strategy Group 1 - FAST Group 2 - ACE	Fine-tuning of initial strategy	Fine-tuning of initial strategy	Program crossover strategy Group 1 - ACE Group 2 - FAST	Fine-tuning of crossover strategy	Fine-tuning of crossover strategy	Program ACE; counsel use of personal processor (both groups)
Clinical Audiological Testing	X				X			X
Sound Quality Ratings					X			
Battery Life Questionnaire				X			X	
Quality and Speech Understanding Questionnaire							X	

Testing either at Clinical Sites or at Denver Research & Technology Labs (Cochlear Americas)								
	Visit 1	Visit 2	Visit 3	Visit 4	Visit 5	Visit 6	Visit 7	Visit 8
Test	Candidacy	Initial Activation (IA)	1 week (post IA)	1M (post IA)	3M (post IA)	3M plus 1 week (post IA)	4M (post IA)	6M (post IA)
Speech Perception					X			X
Reading Span Test					X			

Table 1. Summary of data collection visits.

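### Reading Span is treated as a baseline covariate and an imputation auxiliary, but it is measured only at Visit 5, after 3 months on the randomised strategy

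*Combined protocol and SAP*

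**What the plan says.** Three places give the Reading Span score a role.

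- SAP 1.6.1 plans univariable and multivariable regressions of the co-primary measures on baseline covariates, and names this score first: "Baseline covariates to be explored include (but are not limited to) working memory score from the Reading Span Test".
- SAP 1.9 puts it in the multiple-imputation model as one of "five auxiliary variables to improve the estimation of missing datapoints (Reading Span score, age, duration of hearing loss", followed by the pre-operative sentence score and duration of hearing aid use.
- Protocol 5.1 acknowledges that maturation continues across the crossover and says that the score "will be included as a statistical covariate to understand differences in adaptation that might be associated with working memory".

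The schedule has one administration. Protocol 5.5.4 states: "Visit 5 will include endpoint speech perception tests, the Reading Span Test, clinical audiological testing, and programming of the crossover strategy". Table 1 (protocol 5.6) agrees: the row "Reading Span Test" has a single mark, under Visit 5, 3 months after initial activation.

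**The concern.** A baseline covariate should be fixed before treatment can act on it. This score is taken after a full period on FAST in Group 1 and on ACE in Group 2, and neither document argues that it is stable over that time or unaffected by the strategy in use. If the strategy did shift the score, a regression on it would carry part of the sequence difference under the name of a subject trait.

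The timing also creates a structural gap. The test shares a visit with the first endpoint tests, so a subject who withdraws before Visit 5 has neither an outcome nor a score. Protocol 9.2 reports that some experienced recipients struggled to adapt to FAST, so early withdrawal could be related to adaptation. Working memory was chosen to shed light on adaptation, yet it is recorded only in those who reach month 3.

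**Working it through.** The plan states no figure on this point, and its sample sizes (8 and 11) do not involve the score. The check is therefore a trace of the schedule, a count, and a short piece of algebra.

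**1. Timing.**
- Visit 1 (protocol 5.3.1) does not include the test: "The candidacy evaluation will include a hearing history, air conduction and bone conduction audiogram, a CNC word test, and an AzBio sentence test".
- Visit 2 starts the randomised strategy: "Procedures will include initial activation and mapping of the first strategy (Group 1 will receive FAST, and Group 2 will receive ACE").
- Visit 5, three months later, includes the test.
- Visit 8 does not include it: "Visit 8 will include endpoint speech perception tests, clinical audiological testing, final programming, and fitting with the patient's personal sound processor".

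So the only value is post-randomisation, and no earlier or later value could replace it.

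**2. Who lacks a score.** The SAP allows for attrition (1.2) but gives no rate. Assume 1 to 4 of 20 leave before Visit 5: 1/20 = 5% and 4/20 = 20%. For these subjects 5 − 1 = 4 of the listed auxiliaries remain. SAP 1.9 does not say whether a missing score is itself imputed.

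**3. Co-primary models.** SAP 1.4.1.1 and 1.4.1.2 adjust for period and sequence with a random subject effect. Reading Span is not in either model, so neither non-inferiority test depends on it.

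**4. Covariate regressions.** The outcomes are the co-primary measures, which are collected only at Visits 5 and 8. A subject who leaves before Visit 5 has no outcome and is absent from an observed-data regression whenever the score is taken. The timing costs these regressions no further subjects. What it affects is the meaning of the covariate.

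**5. Imputation.** Write the listed model for subject i in period j as

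Y_ij = μ + τ·T_ij + π·P_j + σ·S_i + β·R_i + γ′Z_i + e_ij,

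with T = 1 for ACE and 0 for FAST, P period, S sequence, R Reading Span and Z the other four auxiliaries.

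- *Both scores missing (left before Visit 5).* The imputed difference is Y_i,ACE − Y_i,FAST = τ ± π + error difference. The term β·R_i enters both scores equally and cancels, so an observed R_i would hardly move the treatment contrast.
- *Only the month-6 score missing.* One value is imputed, β·R_i does not cancel, and the auxiliary can help. These subjects have the score if they completed Visit 5.
- *With an interaction.* A term δ·R_i·T_ij would leave δ·R_i in the difference, and a Reading Span-by-period term would likewise not cancel. Then R_i would matter for early leavers. SAP 1.9 leaves its predictor list open but names no interaction.

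**6. Remaining uses.** The descriptive baseline table lacks the score for early leavers, and working memory cannot be compared between early leavers and completers.

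**The case against.** The strongest reply is that this is mostly a matter of labelling. Reading Span is a visual task (protocol 5.2.5), so three months on one sound coding strategy is unlikely to change the score much. Every subject is tested at the same time point, and treating working memory as a stable trait is defensible. The score enters only exploratory and sensitivity analyses, four other auxiliaries remain, and standard multiple imputation can handle an incomplete predictor. Moving the test would oblige every clinical site to give it, where some could now leave it to the sponsor's Denver labs.

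Most of this stands, and it limits the point. It does not remove it: the stability assumption is nowhere stated, the handling of a missing score is not specified, and both gaps can be closed at little cost.

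Three stronger readings are tempting. From protocol 5.1 a reader might infer that the primary analysis conditions on a post-randomisation variable; the co-primary model statements in the SAP do not include it. A reader might also infer that the covariate regressions lose early leavers because of the timing; they would be lost anyway, having no outcome. Finally, a reader might infer that the missing-data analysis is badly weakened; under the additive model listed, the score largely cancels from the ACE–FAST contrast for exactly those subjects.

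**Conclusion.** The mismatch between use and schedule is real. A score called baseline is measured once, after three months on the randomised strategy, and is unobserved for everyone who leaves before Visit 5.

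Its reach is limited to the exploratory covariate regressions (interpretation, not subject numbers), the descriptive baseline table, any comparison of early leavers with completers, and the imputation sensitivity analysis. In the last of these, the effect on the treatment contrast is likely small unless a Reading Span interaction is added. The co-primary tests are untouched.

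The 5% to 20% without a score rests on an assumed 1 to 4 early leavers. The likely small effect on the contrast rests on reading SAP 1.9 as additive. Any effect of strategy on the score itself is probably small, but the documents give no figure. This is a worthwhile, cheap improvement rather than a threat to the trial's conclusions.

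**What to change.** Give the Reading Span Test at Visit 1 after consent (protocol 14.0 requires consent before any study-related examination), or at Visit 2 before activation. Update Table 1, the Visit 1 or Visit 2 text (5.3.1 or 5.5.1) and section 5.5.4. The score is then a true pre-treatment value, observed for all who are tested at Visit 1, or for all who reach activation if Visit 2 is chosen. SAP 1.6.1 and 1.9 can stand as worded.

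The cost is modest. No test is added, and the protocol already permits this one at clinical sites. Every site must be able to give it, however, including those that would have used the Denver labs, and a few subjects who never reach month 3 will also be tested.

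For subjects already past activation, describe the score in SAP 1.6.1 as a month-3 subject characteristic rather than baseline, with a sentence justifying the assumption that strategy does not affect it. State in SAP 1.9 that missing scores are imputed jointly with the endpoints. This costs wording only.

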1.6.2 Supportive Efficacy Analyses

Additional supportive analyses may also be conducted. These may include, but are not limited to, acute sound quality ratings conducted at the crossover appointment and clinical audiological testing including sound field thresholds and AzBio sentences. All supportive analyses will be clearly described as such.

1.7 Justification of Pooling Across Study Sites

Pooling data from study sites will be done based on the following: all sites will have the same protocol, the sponsor will monitor the sites to assure protocol compliance, and the data gathering mechanism (case report forms and data acquisition) will be the same across all study sites.

Consistency of the primary efficacy endpoints will be assessed by testing for a difference between sites in the difference between FAST and ACE for CNC word recognition and BKB sentence reception in noise. Testing will be conducted via an analysis of variance model, with difference between FAST and ACE as the outcome and site as the factor. A p-value for the site factor of less than 0.15 will be considered evidence of differences between sites for one of the primary efficacy endpoints. If there is evidence of a difference, additional analyses will be performed to explore the possible role of baseline characteristics to explain the results. Results for the primary efficacy endpoint will also be presented separately by site, irrespective of the test of differences between sites, to help understand both qualitative and non-significant differences between sites.

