1.4.1 Primary Efficacy Objectives

The two co-primary efficacy endpoints will be based on analyses of CNC word recognition and BKB sentence reception in babble and speech-shaped noise after 3 months of experience with each strategy (collected at 3-months and 6-months post initial activation). The objective of the two co-primary efficacy endpoints is to test for non-inferiority of FAST compared to ACE. Study success will be defined by rejection of the null hypotheses for both of the two co-primary endpoints.

1.4.1.1 *First Co-Primary Efficacy Endpoint: CNC Word Recognition*

The objective of the first co-primary efficacy analysis is to demonstrate non-inferiority of FAST compared to ACE for word recognition in quiet as evaluated with the CNC test. Success for the first co-primary endpoint will be based on rejection of the null hypothesis of inferiority, with a non-inferiority margin of 10 rau based on clinical judgment and variability observed in previous studies ($M_2 = 10$). The treatment effect will be estimated using a LMM adjusted for period and sequence and a random effect for subject. If the upper 97.5% confidence bound is less than 10 rau, statistical significance will be met at the 0.025 alpha level. The first co-primary endpoint is represented by the following hypotheses:

$$H_0: CNC_{diff} \geq 10 \text{ rau},$$

$$H_a: CNC_{diff} < 10 \text{ rau},$$

where:

CNC_{diff} = ACE – FAST treatment difference, controlling for period and sequence effects, for CNC word recognition in rationalized arcsine units (rau).

1.4.1.2 *Second Co-Primary Efficacy Endpoint: BKB Sentence Reception in Noise*

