1.8 Justification of Pooling Across Devices

Pooling data from subjects with different internal devices (CI24RE, CI512, and CI532) will be done based on the following: all devices included in this study use a perimodiolar electrode and are similar in function, and the co-primary efficacy endpoints are based on within-subject comparisons for which the device remains constant.

Consistency of the primary efficacy endpoints will be assessed by testing for a difference across devices in the difference between FAST and ACE for CNC word recognition and BKB sentence reception in noise. Testing will be conducted via an analysis of variance model, with difference between FAST and ACE as the outcome and device as the factor. A p-value for the device factor of less than 0.15 will be considered evidence of differences across devices for one of the primary efficacy endpoints. If there is evidence of a difference, additional analyses will be performed to explore the possible role of baseline characteristics to explain the results. Results for the primary efficacy endpoints will also be presented separately by device, irrespective of the test of differences across devices, to help understand both qualitative and non-significant differences across devices.

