8.0 Data Analysis

8.1 Statistical Analysis

Endpoint speech perception data will be analyzed using linear mixed models (LMM) in order to test for treatment effects while controlling for period and sequence effects. Non-inferiority will be tested with the confidence intervals of the treatment effects from the statistical models. If the one-sided limit of the 97.5% confidence bound does not exceed the non-inferiority margin, statistical

CONFIDENTIAL

significance will be met at the 0.025 alpha level. The non-inferiority margin for word recognition is 10 rationalized arcsine units (rau). The non-inferiority margin for the sentence in noise tests with an adaptive SNR is –2dB. The non-inferiority margins are based on clinical judgment and variability observed in previous studies testing FAST and ACE.

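### The site and device consistency ANOVAs leave out sequence group, so a learning gain between periods can make them under-flag or over-flag differences (optional, low-cost change)

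*Combined protocol and SAP*

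**What the plan says.** SAP 1.7 assesses consistency across sites with an ANOVA on the within-subject strategy difference: "Testing will be conducted via an analysis of variance model, with difference between FAST and ACE as the outcome and site as the factor". SAP 1.8 repeats this across the three implant types, "with difference between FAST and ACE as the outcome and device as the factor". In both, p below 0.15 counts as evidence of a difference. The consequence is exploratory: "If there is evidence of a difference, additional analyses will be performed to explore the possible role of baseline characteristics to explain the results". The covariates listed in SAP 1.6.1 ("Baseline covariates to be explored include (but are not limited to) working memory score from the Reading Span Test", then age, duration of hearing loss and others) do not name sequence group, though the list is open-ended.

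The results are also shown whatever the p-value: "Results for the primary efficacy endpoint will also be presented separately by site, irrespective of the test of differences between sites", and for devices "Results for the primary efficacy endpoints will also be presented separately by device, irrespective of the test of differences across devices".

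The co-primary analysis treats the same contrast differently. SAP 1.4.1 states: "The treatment effect will be estimated using a LMM adjusted for period and sequence and a random effect for subject". Protocol 8.1 says mixed models are used "in order to test for treatment effects while controlling for period and sequence effects". Protocol 5.1 assigns half the subjects to each order at random, mentions no stratification by site or device, and concedes that changing strategy at month 3 does not remove maturation.

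**The concern.** The subjects are newly implanted and are compared at 3 and 6 months after activation, so some improvement between the two tests is plausible. In a two-period crossover, a period effect appears in the within-subject difference as a contrast between the sequence groups. The primary model removes it; the consistency ANOVAs do not.

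The error then depends on how the two orders happen to fall across sites or devices. Near balance, learning sits in the residual and hides real differences. With imbalance, learning sits in the site or device mean square and produces a flag. Such a flag would send the analyst to baseline characteristics when the cause is the order of treatment. These ANOVAs are the plan's only formal check that the effect is consistent across sites and devices.

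**Working it through.** **Inputs from the documents.** 20 subjects, half per sequence; up to seven sites (protocol synopsis); three devices; flag at p<0.15; SD 7.20 rau for CNC and 1.84 dB for SRT (SAP 1.2, protocol 8.2).

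**Assumed, because the documents give no figure.** The period-2 gain g, the site and device sizes, and the size of any true site or device difference.

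**The plan's own figure.** A paired t-test (one-sided 0.025, true difference 0) with margin/SD = 10/7.2 has power 0.862 at n=7 and 0.918 at n=8. With 2/1.84 the power is 0.863 at n=10 and 0.900 at n=11. This reproduces the stated 8 and 11, so 7.20 is read as the SD of differences.

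**Mechanism.** Let d = FAST - ACE, with treatment effect τ. Group 1 (FAST first) has mean d = τ - g and Group 2 has mean d = τ + g. For SRT, where lower is better, the signs reverse. Code s = ±1 by sequence and let B = Σ nᵢ(site mean of s)². With k sites and no true site effect, the expected mean squares are:

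- between sites: SD² + g²B/(k-1)
- within sites: SD² + g²(20-B)/(20-k)

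The F ratio is doubly noncentral, with noncentralities g²B/SD² and g²(20-B)/SD².

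**Two allocations** (six sites of 3 and one of 2; SD² = 51.84; g = 5):

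- Group 1 counts 2,2,2,1,1,1,1: B = 6×3×(1/3)² = 2. Between: 51.84 + 25×2/6 = 60.2. Within: 51.84 + 25×18/13 = 86.5. False-flag rate 0.050 (0.003 at g = 10).
- Group 1 counts 3,0,3,0,2,1,1: B = 4×3 + 2×3×(1/3)² = 12.67. Between: 51.84 + 25×12.67/6 = 104.6. Within: 51.84 + 25×7.33/13 = 65.9. False-flag rate 0.361 (0.678 at g = 10).

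Simulation (100,000 runs per allocation) agrees: 0.049 and 0.365 at g = 5. With sequence in the model all rates are 0.150 to 0.152.

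**All 10:10 allocations, seven sites, exact, nominal rate 0.15:**

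| Gain (rau) | 5th-95th percentile of rate | Allocations outside 0.10-0.20 |
|---|---|---|
| 2 | 0.13-0.19 | 1% |
| 3 | 0.10-0.23 | 24% |
| 5 | 0.05-0.33 | 67% (43.4% below, 23.5% above) |
| 10 | 0.00-0.61 | 67% |

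The mean over allocations stays at 0.150 to 0.154. Other layouts at 5 and 10 rau:

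- five sites of 4: 0.08-0.37 and 0.02-0.68
- four sites of 5: 0.07-0.31 and 0.01-0.53
- devices split 7/7/6: 0.07-0.36 and 0.01-0.64

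**Detection at p<0.15, averaged over allocations** (40,000 runs per cell; seven sites, or devices 7/7/6):

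| True difference | g=0 | 2 | 3 | 5 | 10 | With sequence |
|---|---|---|---|---|---|---|
| Site SD 7.2 rau | 0.79 | 0.77 | 0.75 | 0.68 | 0.46 | 0.77-0.78 |
| Site SD 5 | 0.58 | 0.56 | 0.52 | 0.46 | 0.30 | 0.55-0.56 |
| Site SD 3 | 0.33 | 0.31 | 0.30 | 0.27 | 0.21 | 0.31-0.32 |
| One device off by 10 rau | 0.86 | 0.83 | 0.80 | 0.72 | 0.47 | 0.83-0.84 |
| One device off by 5 rau | 0.41 | 0.39 | 0.38 | 0.32 | 0.23 | 0.39-0.40 |

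For SRT with site SD 1.28 dB, gains of 0/0.5/0.77/1.28/2.55 dB give 0.58/0.55/0.53/0.46/0.31, against 0.55 with sequence.

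**The case against.** Over the randomisation the false-flag rate is right, about 0.15 at every gain considered. The SAP offers 0.15 as a screening cut-off and promises no error rate conditional on the realised allocation. This stands: on average the harm is lost sensitivity only. But the trial will have one allocation, with known sequence counts, and there the error can go either way.

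Nothing is decided by these tests. Pooling is justified on other grounds, study success rests on the co-primary models, and the by-site and by-device results appear regardless. This also stands and sets the priority.

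The gain is assumed, and 5 rau is not a sharp threshold. The distortion depends on g/SD, and SAP 1.2 itself allows for more variability than expected. With SD 10 rau and a 5 rau gain, the seven-site range narrows to 0.08-0.26 and the share of allocations outside 0.10-0.20 falls from 67% to 39%. The effect shrinks but does not vanish.

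The SAP could be read as allowing adjustment, since it assesses consistency of endpoints that are defined as period- and sequence-adjusted. But it names site or device as the factor and no other term, so the natural reading is a one-way ANOVA.

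**Conclusion.** The point holds as a low-priority improvement. As written, the two ANOVAs do not adjust for an effect that the primary model removes and the protocol says is not eliminated. If the gain is about 5 rau and the SD of differences is 7.2 rau, the false-flag rate in about two thirds of seven-site allocations lies outside 0.10-0.20, and average detection of a site SD of 5 rau falls from 0.58 to 0.46. At 2 rau or less the omission is harmless. At site SDs of 2 to 3 rau the test is weak with or without sequence. The figures rest on assumed gains, layouts and effect sizes, on unstratified 10:10 assignment, and on a period effect common to all sites and devices. The co-primary conclusions are not affected.

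**What to change.** In SAP 1.7 and 1.8, add sequence group as a second factor and test site (or device) adjusted for it. Alternatively, test site-by-treatment and device-by-treatment in the primary mixed model with the site or device main effect included; this matches the ANOVA only when all pairs are complete. State that by-site and by-device results are period-adjusted estimates with 95% confidence intervals, and tabulate Group 1 and Group 2 counts by site and device.

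The cost is SAP wording and code, with no new data. One residual degree of freedom is lost (13 to 12 for seven sites, 17 to 16 for three devices), which lowers detection by about 0.02 if there is no gain. The common period effect cannot be checked at a site with only one sequence. Site estimates stay imprecise. The 95% half-width is t(0.975, 12) × 7.2 × √(1/3 + m²/W), where m is the site mean of s and W = 20 - B. In an allocation with W = 12.7, a 3-subject site has a half-width of 9.2 rau with both sequences (m = 1/3) and 10.1 rau with one (m = 1).
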